Annually, approximately 15 million babies worldwide are born preterm [1, 2]. Preterm birth is a leading cause of neonatal mortality and morbidity [3]. Cervical insufficiency is one factor implicated in the complex mechanisms involved in spontaneous preterm birth [4]. Cervical insufficiency is characterized by acute and painless dilatation of cervix in absence of uterine contractions resulting in the inability of cervix to retain a pregnancy to term. Insertion of a cervical cerclage suture can be used to treat cervical insufficiency. A cervical cerclage is a mechanical support to the cervix, where a surgical band or string is applied around the cervix to prevent preterm opening of the cervix, and thereby preventing preterm birth. It can be applied either vaginally or trans-abdominally. The latter can be applied either by laparoscopic or open access surgery. Growing evidence support that both open access and laparoscopic cerclage procedures are safe and effective [5]. Still, many aspects of the abdominal cerclage remains uncertain. Recently, a study by Ades et al. was published on the obstetric outcome of subsequent pregnancies in women from an Australian single-center cohort who had a laparoscopic cerclage left in situ [6]. They reported on 22 women who became pregnant a second or third time after a laparoscopic cerclage. The authors encouraged other groups to report their obstetric outcomes on subsequent pregnancies after laparoscopic cerclage in order to gather a larger data material to describe this gap in evidence. Therefore, we plan to study the obstetric outcome from the first and subsequent pregnancies after laparoscopic cerclage in a Danish cohort from Aarhus University Hospital in a 10 years' period.

Objective

In a Danish cohort, to investigate the obstetric outcome after laparoscopic cerclage placement in the first and subsequent pregnancies.

Material and Methods

Study type

Observational study based on medical chart review.

Eligibility criteria

Women who underwent laparoscopic cerclage at Aarhus University Hospital, Denmark between May 2011 and May 2021. Trachelectomy prior to the laparoscopic cerclage is defined as an exclusion criteria.

The laparoscopic cerclage procedure

The surgical method of the laparoscopic cerclage procedure at Aarhus University Hospital is previously described in a paper by Riiskjaer et al [7]. The primary surgeon has been one of three laparoscopic surgeons with a long experience in performance of the procedure.

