- History of three or more spontaneous miscarriages/deliveries between 14+0 and 36+6 weeks
- Other (free text)

Characteristics of the surgical procedure

- Additional procedures performed during surgery (e.g. hysteroscopy, removal of endometriosis)
- Performed in Day Surgery (yes/no)
- Date of surgery (dd-mm-yyyy)
- Early complications from the laparoscopic cerclage (follow-up time is 30 days from the procedure):
 - Conversion to laparotomy during surgery (yes/no)
 - Haemorrhage > 500 ml (yes/no)
 - Postoperative infection treated at hospital (yes/no)
 - Damage to internal organs (yes/no)
 - Need for re-operation (yes/no)
 - Admission to Intensive Care Unit (yes/no)
 - Thromboembolic events (defined as deep vein thrombosis, pulmonary embolism or stroke) (yes/no)
 - Maternal cardiopulmonary arrest (yes/no)
 - Maternal death (yes/no)
- Late complications from the laparoscopic cerclage (follow-up in the entire period of data collection subsequent to the laparoscopic cerclage):
 - Erosion into the vagina treated in hospital (yes/no)
 - Pain complaints from the stiches leading to intervention in pregnancy (yes/no)
 - Other complications from the cerclage leading to intervention in hospital (free text)

For every known/confirmed pregnancy subsequent** to the laparoscopic cerclage (follow-up in the entire period of data collection subsequent to the laparoscopic cerclage):*

**defined as a pregnancy confirmed by urine and/or serum hcg and/or ultrasound AND described in the medical record*

***If the laparoscopic cerclage was performed in early pregnancy, this pregnancy is the first pregnancy for data collection*

- Pregnancy;
 - Maternal age (years)
 - Parity (numerical)
 - Conceivement (Spontaneous/Assisted Reproductive Technologies)
 - Certain gestational age, defined as gestational age determined by Crown-Rump-Length (yes/no)
 - Gestation (singleton/multiple)

- Treatment with vaginal progesterone (yes/no)
- At miscarriage or delivery;
 - Gestational age (weeks and days)
 - If gestational age < 22 weeks and 0 days of gestation;
 - Need for operative surgery in connection with miscarriage (yes/no)
 - If gestational age ≥ 22 weeks and 0 days;
 - Administration of lung maturation < 34 weeks of gestation (yes/no)
 - Administration of tocolytics < 34 weeks of gestation (yes/no)
 - Chorioamnionitis (defined as antibiotic treatment or intervention leading to delivery)

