- Prior versus no prior cesarean delivery at time of laparoscopic abdominal cerclage
- Prior versus no prior conisation at time of laparoscopic abdominal cerclage
- Placement of laparoscopic abdominal cerclage before or during early pregnancy

STATA will be used for data management and analyses.

Data collection

Prior to data collection the relevant authority (Central Denmark Region) will be applied for permission to access the relevant data source. All data is already available and will be extracted from the patients' electronic data records. Women will be identified on the ICD-10 Procedure Code KLDD10B. The follow-up period extends to May 2022 to allow at least one year of follow-up for all procedures. The primary investigator performs a pilot collection of data from the electronic data records of ten random women in the data set giving birth at Aarhus University Hospital. The pilot collection aims to test the accessibility of the variables, the use of the eCRFs, and the time spent. Following the pilot of data collection, the study group meet to adjust the variables if needed.

Data management

All data will be entered in to an eCRF designed for this study using the REDCap database Study. Data will be collected and managed using REDCap electronic data capture tools hosted at Aarhus University [9]. REDCap is a secure, web-based application designed to support data capture for research studies, providing 1) an intuitive interface for validated data entry; 2) audit trails for tracking data manipulation and export procedures; 3) automated export procedures for seamless data downloads to common statistical packages; and 4) procedures for importing data from external sources.

Data will be handled according to all relevant Danish laws including the General Data Protection

Regulation (“Databeskyttelsesforordningen”) and the Data Protection Act (“Databeskyttelsesloven”). The project is registered with the Central Denmark Region’s internal list of research projects.

Publication plan

Results from this study will be published in a peer-reviewed journal.

The principal investigator will draft the paper as first author, and the daily supervisor will be last corresponding author. Additional authorship will follow standard authorship guidelines and will include all members of study group. Authorships of additional publications will depend on the nature of involvement.

Confidentiality

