## Statistical analysis plan

Statistics will be descriptive and data will be presented with counts and percentages for categorical variables, mean and standard deviation for continuous Gaussian distributed variables, and median and interquartile range for continuous non-Gaussian variables. Proportions will be presented with a 95% confidence interval for the dichotomous outcomes.

Subgroup analyses of the primary outcome will be undertaken for the following subgroups:

- Prior versus no prior cesarean delivery at time of laparoscopic cerclage
- Prior versus no prior conisation at time of laparoscopic cerclage
- Placement of laparoscopic abdominal cerclage before or during early pregnancy

STATA will be used for data management and analyses.

Examples of anticipated tables is shown below.

**Table 1.** Maternal Characteristics upon laparoscopic cerclage placement

n	n
Age, years	mean (range)
Smoking	no. (%)
Body Mass Index (kg/m  )	median (interquartile range)
Parity	median (interquartile range)
Previous conization	no. (%)
- 0	no. (%)
- 1 conus	
- 2+	
Previous caesarean delivery	
Performed as emergency caesarean	no. (%)
Previous uterine surgery	no. (%)
Placement of laparoscopic cerclage during pregnancy	no. (%)
Indications for the laparoscopic cerclage placement	
a) Previous emergency/laboring cesarean delivery followed by a spontaneous singleton late miscarriage or preterm birth from 16+0 to 28+0 weeks	no. (%)
b) Previous elective vaginal cerclage placement but nonetheless a spontaneous late miscarriage or preterm birth between 14+0 and 28+0 weeks (= failed vaginal cerclage)	no. (%)
c) Previous ultrasonography-indicated emergency cerclage with preterm birth between 14+0 and 28+0 weeks	no. (%)
d) Conization and a short pre-pregnancy cervix	no. (%)
e) Two or more deliveries in gestational age 16+0 to 28+0 weeks and a clinical diagnosis of cervical insufficiency	no. (%)
f) Three or more deliveries in gestational age 16+0 to 36+6 weeks	no. (%)
g) Others	no. (%)

**Table 2.** Characteristics laparoscopic cerclage procedure

n		n
Additional procedures performed during surgery		no. (%)
Performed in Day Surgery		no. (%)
Year of surgery		
2011 trough 2014		no. (%)
2015 trough 2018		no. (%)
2019 trough 2022		no. (%)
Early complications		
Conversion to laparotomy during surgery		no. (%)
Haemorrhage > 500 ml		no. (%)
Postoperative infection treated at hospital		no. (%)
Damage to internal organs		no. (%)

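### The cohort is found through one procedure code that is not shown to retrieve converted operations, so the reported conversion rate may be too low

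*Protocol*

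**What the plan says.** The protocol's Eligibility criteria section defines the target population as "Women who underwent laparoscopic cerclage at Aarhus University Hospital, Denmark between May 2011 and May 2021", with previous trachelectomy excluded. The Data collection section gives the method of finding these women: "Women will be identified on the ICD-10 Procedure Code KLDD10B". No second code, operating list, surgeon list or free-text search is named in either document.

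Under Characteristics of the surgical procedure, the protocol lists conversion to laparotomy as a yes/no item among the early complications, which are followed for 30 days. SAP Table 2 carries the row "Conversion to laparotomy during surgery" with a count and percentage. The SAP describes the analysis as descriptive throughout.

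The one check on data collection is a pilot in "ten random women in the data set giving birth at Aarhus University Hospital". Its purpose is stated: "The pilot collection aims to test the accessibility of the variables, the use of the eCRFs, and the time spent". After it, the study group may adjust the variables.

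**The concern.** Conversion is both something the study reports and something that could decide whether a woman is found. The protocol's introduction recognises two routes for abdominal cerclage, laparoscopic and open. A converted operation starts by one and ends by the other, so it could plausibly be filed under a different code. In that case the search selects on the outcome, and a low or zero count in Table 2 could come from the search alone. A reader could not tell that zero from a true one.

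The eligibility wording does not settle the matter either, since it does not say whether an operation begun laparoscopically and then converted or abandoned counts as a laparoscopic cerclage. What is at stake is the conversion figure and the denominator of the safety table for a ten-year single-centre series. Placements in early pregnancy raise a related question. Timing of placement is a planned subgroup, and the documents do not say whether such operations carry the same code.

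**Working it through.** **What the documents supply.** One code, one hospital, May 2011 to May 2021, and conversion as a reported item. They give no sample size, expected conversion rate, complication rate or coding completeness, so there is no figure of the plan's to reproduce. Every rate below is an assumption chosen to show direction and size.

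**Can the pilot reveal missed women?** No. It samples women already in the data set, so every one of them was found by the code. It tests access to variables, use of the eCRF and time spent, not completeness.

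**Conversion rate.** Let t be the true conversion rate, s1 the share of converted operations that the code finds, and s0 the share of all other operations that it finds. Then

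observed rate = t·s1 / [t·s1 + (1 − t)·s0]

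| Assumed capture | t = 1% | t = 2% | t = 5% |
|---|---|---|---|
| Half of conversions found, all others found (s1 = 0.5, s0 = 1) | 0.50% | 1.01% | 2.56% |
| No conversions found, all others found (s1 = 0, s0 = 1) | 0% | 0% | 0% |
| 90% found in both groups (s1 = s0 = 0.9) | 1% | 2% | 5% |
| All conversions found, 90% of others (s1 = 1, s0 = 0.9) | 1.11% | 2.22% | 5.52% |

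For example, with t = 2% and half missed: 0.02 × 0.5 / (0.02 × 0.5 + 0.98) = 0.010 / 0.990 = 1.01%. The third row shows that loss unrelated to outcome leaves the rate unchanged. The fourth shows that the opposite pattern raises it.

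**Other complications.** Let c be the conversion rate, m the share of converted operations missed, and a and b the complication rates in converted and non-converted operations. Then

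observed rate = [c(1 − m)a + (1 − c)b] / (1 − c·m), and true rate = c·a + (1 − c)b

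Take a = 30%, b = 3%:

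| c | True rate | Observed, half missed | Observed, all missed |
|---|---|---|---|
| 1% | 3.27% | 3.14% | 3.00% |
| 2% | 3.54% | 3.27% | 3.00% |
| 5% | 4.35% | 3.69% | 3.00% |

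Even with a tenfold excess and every conversion missed, the shift is 0.27 to 1.35 percentage points. If a = b = 3%, the observed and true rates are both 3.0%.

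**Would a confidence interval protect the reader?** Not reliably. Suppose 100 operations are found and none is a conversion. The exact 95% upper limit is 1 − 0.025^(1/100) = 3.6%. If 1, 3 or 5 conversions were all missed, the true proportions would be 1/101 = 1.0%, 3/103 = 2.9% and 5/105 = 4.8%. The interval covers the first two and not the third, because it reflects sampling error and not lost cases. This is a worst case, since it assumes that every conversion is missed.

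**The case against.** The strongest reply is that the mechanism depends on coding practice that the documents do not describe. If a converted operation keeps KLDD10B, nothing is lost. The plan also lists conversion as an item to collect, which suggests that its authors expect converted operations in the cohort, and the eligibility wording speaks of undergoing the procedure, not of completing it. Both points stand against any statement that the search does select on completed procedures. Neither shows that the code retrieves conversions.

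It can also be said that surgical complications are secondary here. The objective is obstetric outcome, and conversion sits among the procedural characteristics, outside the Outcomes section. That is fair, and it limits the importance of the point. The safety table will still be published and read.

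A reader might infer that the single code biases conversion and complication rates towards zero, or that any operation filed elsewhere does so. The documents do not support either inference: they do not define the code, and the direction of bias depends on which operations are lost. A reader might also infer that the early-pregnancy subgroup is depleted. That is possible but not shown, and a smaller subgroup is not in itself a biased one.

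**Conclusion.** The point holds in conditional form. Case-finding rests on one code, conversion is a reported item, and nothing in the plan shows that the code retrieves converted operations or would reveal those it missed. If converted operations are filed under another code, the conversion rate is underestimated: roughly halved if half are missed, and zero by construction if all are. Other complication rates are affected only if the missed women had more complications, and then modestly when conversion is rare. All the rates used are assumptions.

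This is a cheap improvement to case-finding, not a demonstrated bias. It might seem to follow that the whole cohort should be redefined as every woman in whom a laparoscopic cerclage was attempted. That goes too far, because it would change the population for the obstetric analyses, whose stated subject is pregnancy after cerclage placement.

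**What to change.** - State in the protocol how converted and abandoned operations, and placements in early pregnancy, are coded at the hospital.
- Besides KLDD10B, query the hospital's codes for open abdominal cerclage, cerclage in pregnancy and conversion for May 2011 to May 2021. Check the result against the operating list of the three surgeons.
- Include operations begun laparoscopically and converted in the Table 2 denominator.
- Count abandoned operations in Table 2 only, and keep the obstetric analyses to women with a cerclage placed.
- Report how many women each source adds. If the answer is none, that supports the conversion figure.

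The cost is a few extra code queries, a short chart check at one hospital and possibly an extension of the data-access permission, since the protocol ties that permission to the relevant data source and mentions no operating list.

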### Conflicts of interest

The members of the study group have no conflicts of interest to declare. The study sponsor has no ultimate authority over any aspects of the study design, conduct, or reporting.

### Trial registration

The study is registered at [clinicaltrials.gov](https://clinicaltrials.gov) using the administrative authorities of Aarhus University (UAarhus). NCT05863481.

### Funding

Funding for the study is provided as a part of a larger grant by the Novo Nordic Foundation.

## Statistical analysis plan

Statistics will be descriptive and data will be presented with counts and percentages for categorical variables, mean and standard deviation for continuous Gaussian distributed variables, and median and interquartile range for continuous non-Gaussian variables. Proportions will be presented with a 95% confidence interval for the dichotomous outcomes.

Subgroup analyses of the primary outcome will be undertaken for the following subgroups:

- Prior versus no prior cesarean delivery at time of laparoscopic cerclage
- Prior versus no prior conisation at time of laparoscopic cerclage
- Placement of laparoscopic abdominal cerclage before or during early pregnancy

STATA will be used for data management and analyses.

Examples of anticipated tables is shown below.

**Table 1.** Maternal Characteristics upon laparoscopic cerclage placement

n	n
Age, years	mean (range)
Smoking	no. (%)
Body Mass Index (kg/m  )	median (interquartile range)
Parity	median (interquartile range)
Previous conization	no. (%)
- 0	no. (%)
- 1 conus	
- 2+	
Previous caesarean delivery	
Performed as emergency caesarean	no. (%)
Previous uterine surgery	no. (%)
Placement of laparoscopic cerclage during pregnancy	no. (%)
Indications for the laparoscopic cerclage placement	
a) Previous emergency/laboring cesarean delivery followed by a spontaneous singleton late miscarriage or preterm birth from 16+0 to 28+0 weeks	no. (%)
b) Previous elective vaginal cerclage placement but nonetheless a spontaneous late miscarriage or preterm birth between 14+0 and 28+0 weeks (= failed vaginal cerclage)	no. (%)
c) Previous ultrasonography-indicated emergency cerclage with preterm birth between 14+0 and 28+0 weeks	no. (%)
d) Conization and a short pre-pregnancy cervix	no. (%)
e) Two or more deliveries in gestational age 16+0 to 28+0 weeks and a clinical diagnosis of cervical insufficiency	no. (%)
f) Three or more deliveries in gestational age 16+0 to 36+6 weeks	no. (%)
g) Others	no. (%)

**Table 2.** Characteristics laparoscopic cerclage procedure

n		n
Additional procedures performed during surgery		no. (%)
Performed in Day Surgery		no. (%)
Year of surgery		
2011 trough 2014		no. (%)
2015 trough 2018		no. (%)
2019 trough 2022		no. (%)
Early complications		
Conversion to laparotomy during surgery		no. (%)
Haemorrhage > 500 ml		no. (%)
Postoperative infection treated at hospital		no. (%)
Damage to internal organs		no. (%)
Need for re-operation		no. (%)
Admission to Intensive Care Unit		no. (%)
Thromboembolic events		no. (%)
Maternal cardiopulmonary arrest		no. (%)
Maternal death		no. (%)
Late complications		
Erosion into the vagina treated in hospital		no. (%)
Pain complaints from the stiches leading to intervention in pregnancy		no. (%)
Other complications from the cerclage leading to intervention in hospital		no. (%)

**Table 3.** Pregnancy outcomes and neonatal survival subsequent to laparoscopic cerclage placement

Obstetric outcome in pregnancies treated with laparoscopic cerclage  
Statistical analysis plan version 1.0

**Table 4.** Time intervals

n	n
Time from the laparoscopic cerclage to first pregnancy (years and days)	median (IQR)

**Table 5.** Characteristics of live born neonates

n	n
Gestational age at birth	no. (%)
Birth weight (g)	median (IQR)

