Variables and outcomes

Below is provided an overview of the included variables collected from the in-hospital electronical medical chart.

Demographics and obstetric history

Maternal characteristics at time of laparoscopic cerclage:

- Maternal age (years)
- Parity (reflect the number of births ≥ 22 gestational weeks)
- Body mass index (BMI) (kg/m²)
- Smoking (yes/no)
- Trachelectomy (yes/no)
- Previous caesarean delivery (yes/no)
 - If yes; Planned or non-laboring (cervical dilatation <4cm)/Laboring caesarean delivery with cervical dilatation > 4cm and <10cm/Laboring caesarean delivery at full cervical dilatation
 - If laboring; cervical dilatation prior to the caesarean section (cm)
 - If yes; indication (labour dystocia/fetal distress/maternal request/non-cephalic presentation/extensive vaginal bleeding/maternal medical complication/other)
- Previous cervical conisation (0/1/2/3 or 4)
- Previous surgery of the uterine wall (yes/no)
 - If yes; myomectomy/sepum resection/other
- Timing of laparoscopic cerclage (before conception/in early pregnancy)
 - If in early pregnancy; gestational age at cerclage placement
- Indication for the laparoscopic cerclage placement as stated by the clinician;
- in the following, the presumption is that the miscarriages/deliveries is likely to be associated with cervical insufficiency (more than one answer is allowed)
 - History of laboring cesarean delivery (>4cm dilated) followed by a spontaneous singleton miscarriage/delivery between 14+0 and 28+0 weeks
 - History of laboring cesarean delivery (>4cm dilated) followed by a spontaneous singleton delivery between 28+1 and 34+0 weeks
 - History with a prior elective vaginal cerclage but nonetheless a spontaneous miscarriage/ delivery between 14+0 and 28+0 weeks
 - History with a prior elective vaginal cerclage but nonetheless a spontaneous delivery between 28+1 to 34+0 weeks
 - History of a previous emergency cerclage with but nonetheless a spontaneous miscarriage/ delivery between 14+0 and 28+0 weeks
 - History of a previous emergency cerclage with a spontaneous delivery between 28+1 and 34+0 weeks
 - Any conization and a short pre-pregnancy cervix
 - Any conization and one or more spontaneous miscarriages/deliveries between 14+0 and 28+0 weeks
 - Any conization and one or more deliveries between 28+1 and 34+0 weeks
 - History of two or more spontaneous miscarriages/deliveries between 14+0 and 28+0 weeks

- History of two or more deliveries between 28+1 and 34+0 weeks

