- Indication for delivery (spontaneous labor contractions/PPROM/PROM/obstetric indication/abdominal cerclage as indication for delivery)

Outcomes

The outcomes of this study apply to a set of core outcomes for evaluation of interventions to prevent preterm birth leaving out the late neurodevelopmental morbidity [8].

Maternal:

- Pregnancy and delivery (follow-up in the entire period of data collection subsequent to the laparoscopic cerclage):
 - Time from the laparoscopic cerclage to first known/confirmed pregnancy (counting from the first day in pregnancy based on results from ultrasonography if available, otherwise on the date of her last menstrual period)
 - Pregnancies subsequent to the laparoscopic cerclage (numerical)
 - Miscarriages
 - Early miscarriages (< 16 weeks and 0 days)
 - Late miscarriages (< 22 weeks and 0 days)
 - Deliveries < 28 weeks and 0 days of an infant living at time of discharge from hospital
 - Deliveries < 32 weeks and 0 days of an infant living at time of discharge from hospital
 - Deliveries < 34 weeks and 0 days of an infant living at time of discharge from hospital
 - Deliveries < 37 weeks and 0 days of an infant living at time of discharge from hospital
 - Uterine rupture (yes/no)

Neonatal:

The following neonatal outcomes are reported for neonates delivered with a gestational age ≥ 20 weeks and 0 days.

- Gestational age (weeks and days)
- Birthweight (g) (follow-up at delivery)
- Neonatal survival (defined as survival at time of discharge from hospital)
- Survival with major neonatal morbidity (time point: at discharge from hospital)
 - Necrotising enterocolitis (NEC)

- Bronchopulmonary Dysplasia (BPD) (defined as respiratory/oxygen support at postmenstrual age (PMA) 36 weeks)
- Intraventricular haemorrhage (IVH) Grade III and IV
- Hydrocephalus with ventriculoperitoneal (VP) shunt
- Periventricular leukomalacia
- Retinopathy of prematurity (ROP)

Statistical analysis plan

Statistics will be descriptive and data will be presented with counts and percentages for categorical variables, mean and standard deviation for continuous Gaussian distributed variables, and median and interquartile range for continuous non-Gaussian variables. Proportions will be presented with a 95% confidence interval for the dichotomous outcomes '*neonatal survival*' and '*neonatal survival without major neonatal morbidity*'.

Subgroup analyses of the primary outcome will be undertaken for the following subgroups:

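### Time from cerclage to first pregnancy works out negative for cerclages placed in early pregnancy, and nothing in the available text keeps these women out of the single median (IQR) in SAP Table 4

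*SAP*

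**What the plan says.** Four parts of the plan bear on this interval.

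- **Definition.** The protocol's maternal outcomes include the time from the laparoscopic cerclage to the first known or confirmed pregnancy, "counting from the first day in pregnancy based on results from ultrasonography if available, otherwise on the date of her last menstrual period".
- **Which pregnancy is first.** In the protocol's block of variables for each known or confirmed pregnancy after the procedure, a footnote states: "If the laparoscopic cerclage was performed in early pregnancy, this pregnancy is the first pregnancy for data collection".
- **In-pregnancy placements are in the cohort.** The only stated exclusion (protocol, Eligibility criteria) is prior trachelectomy. Timing of placement is recorded as before conception or in early pregnancy and, for the latter, "If in early pregnancy; gestational age at cerclage placement". SAP Table 1 has a row for "Placement of laparoscopic cerclage during pregnancy".
- **Reporting.** SAP Table 4 has one outcome row, "Time from the laparoscopic cerclage to first pregnancy (years and days", summarised by median (IQR), with its own n line and no restriction by timing of placement. The comparison of placement before and during pregnancy belongs to a list introduced by "Subgroup analyses of the primary outcome will be undertaken for the following subgroups". It does not extend to this interval. The table shells are introduced with "Examples of anticipated tables is shown below".

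**The concern.** A waiting time should run forward from surgery. For a woman already pregnant at surgery, the end point falls before the starting point, so the value measures how far along she was and not how long she waited. One median over both groups mixes two quantities.

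Every such value sits at the bottom of the distribution, so the error has one direction: the median and the lower quartile fall. A reader would take the result as the typical wait for pregnancy after the procedure, and it would be too short.

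If the analyst notices the negative values, at least three treatments are open: keep them, leave these women out, or count to their next pregnancy. Each can give a different median, and the choice would be made after seeing the data.

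**Working it through.** The plan gives no figure for this interval, no cohort size and no share treated in pregnancy, so there is nothing of its own to reproduce. The sign follows from the text; the size needs assumptions.

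**1. Sign.** Interval = (first day of first pregnancy) − (date of cerclage). If surgery is done at gestational age G of the pregnancy that counts as first, that pregnancy began G before surgery, so the interval is −G.

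| Assumed gestational age at surgery | Interval, menstrual dating | Interval, if counted from conception (14 days later) |
|---|---|---|
| 6+0 weeks | −42 days | −28 days |
| 10+0 weeks | −70 days | −56 days |
| 12+0 weeks | −84 days | −70 days |
| 14+0 weeks | −98 days | −84 days |

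Both ways of dating give negative values.

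**2. Does anything keep these women out?** The eligibility criteria do not. The subgroup list covers the primary outcome only. Table 4 carries no restriction, and Table 1 only counts these women.

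**3. Effect on the quantiles, with no assumed shape for the waiting times.** Let s be the share treated in pregnancy among women who contribute a value. If their values lie below the preconception values, the reported p-quantile is the (p − s)/(1 − s) quantile of the preconception intervals, for p > s.

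| s (assumed) | Reported median is this preconception quantile | Reported lower quartile is this preconception quantile |
|---|---|---|
| 2% | 0.48/0.98 = 0.490 | 0.23/0.98 = 0.235 |
| 5% | 0.45/0.95 = 0.474 | 0.20/0.95 = 0.211 |
| 10% | 0.40/0.90 = 0.444 | 0.15/0.90 = 0.167 |
| 20% | 0.30/0.80 = 0.375 | 0.05/0.80 = 0.063 |

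Once s exceeds 25%, the lower quartile is itself negative.

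One qualification applies. Under menstrual dating, a cerclage placed after menstruation but before conception in the same cycle also gets a slightly negative value, up to about two weeks. Zero is therefore not an exact dividing line and the percentiles are approximate. The numerical effect is negligible.

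**4. Illustration in days.** Assume exponential preconception intervals with median m. The q-quantile is −ln(1 − q) × m / ln 2.

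| s | Reported median, m = 180 days (fall) | Reported median, m = 365 days (fall) |
|---|---|---|
| 0 | 180 | 365 |
| 2% | 175 (5) | 354 (11) |
| 5% | 167 (13) | 338 (27) |
| 10% | 153 (27) | 310 (55) |
| 20% | 122 (58) | 247 (118) |

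**5. Allowing for the end of follow-up.** Procedures run from May 2011 to May 2021 and follow-up ends in May 2022, so follow-up is about 1 to 11 years. Assume it is uniform over that range, with exponential conception times and a one-year median among eventual conceivers. The median among preconception women with a recorded pregnancy is then 0.900 year. Mixing in 5%, 10% or 20% gives 0.835, 0.767 or 0.617 year. With eventual-conceiver medians from 0.5 to 1.5 years, the fall is 0.04 to 0.09 year at 5%, 0.07 to 0.18 at 10% and 0.16 to 0.38 at 20%. At 2% it is 0.01 to 0.03 year.

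**The case against.** The negative value comes from joining two places. The footnote stands under the pregnancy-level variables and speaks of data collection; the outcome definition does not cite it. The outcome's follow-up heading looks forward from surgery, and a table in years and days suits a forward interval. For a woman already pregnant, the time to first pregnancy could be taken as not applicable. The shells are examples, the n line would accommodate a restricted denominator, and negative durations would be conspicuous in a single-centre chart review. An analyst might well put this right unprompted.

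Part of this stands. A reader might infer that the plan orders negative durations to be pooled, or that the published median will certainly be wrong. The documents do not say that. It also lowers the weight of the point, because the outcome is purely descriptive and the share treated in pregnancy could be very small.

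It does not remove the point. The footnote is the only text that says which pregnancy is first for these women, and it sits under a heading that uses the same known-or-confirmed term as the outcome. Followed literally, the two rules give a negative value, and no other visible text corrects it.

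A reader might also infer that the median is invalid because women without a recorded pregnancy by May 2022 contribute nothing, and that a Kaplan-Meier analysis is needed. The documents do not support that either. A median among women who conceived is a legitimate description. The Kaplan-Meier curve answers a different question, and the listed variables do not include intention to conceive. Pregnancies count only if "defined as a pregnancy confirmed by urine and/or serum hcg and/or ultrasound AND described in the medical record". What remains is a matter of labelling.

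**Conclusion.** The point holds at low severity. The protocol's definition and footnote together give an interval of minus gestational age at surgery for in-pregnancy placements, and no visible text keeps these values out of the single Table 4 median (IQR). The direction needs no assumed number: the median and lower quartile can only be pulled down. The size does need one, because the share treated in pregnancy is not documented. The percentile shifts assume only that share and, to a close approximation, that in-pregnancy values lie below the preconception ones. The figures in days and years also rest on assumed distributions and serve as illustration.

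It would be wrong to conclude that the distortion is known to be large or that the study's main results are at risk. Neonatal survival does not use this interval.

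**What to change.** State in the SAP that the Table 4 row covers only cerclages placed before conception, and give that row its own n. Report in-pregnancy placements separately, by number and gestational age at surgery. Both variables are already collected. Because a placement in the cycle of conception can still give a slightly negative value under menstrual dating, the restriction should use the recorded timing of placement and not the sign of the interval.

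As minor wording, label the median as applying to women with a recorded pregnancy by May 2022, and give the number of preconception women without one. No Kaplan-Meier supplement is needed.

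The cost is one or two SAP sentences and a row label. The downside is that the row rests on slightly fewer women.
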